5.4 Intervention procedures and process evaluation

5.4.1 Intervention procedures

CBDAs linked to PHC clinics allocated to the intervention arm will be provided with training in HIVST and IEC materials including flipboards, used kits to show clients how to interpret positive, negative and inconclusive results, a cotton bud and vial of water to demonstrate the mouth swabbing and development process, leaflets and a buffer stock of OraQuick ADVANCE HIV I/II test kits, to be stored in a locked container in their own home.

Adult (16 years or older) participants wishing to know their status will be provided with brief pre-test counselling together with the kit, and an envelope containing a self-completed

questionnaire for return of the used test, a telephone hotline number, a self-referral slip for the nearest PHC offering ART services in case of a positive result, and information on how to access VMMC for HIV-negative men. The kit contains instructions for use and results interpretation in Chichewa.

Clients will be encouraged to return their used kits confidentially to the CBDA, either in person or by posting in the sealed envelope into an opaque locked "ballot box" container kept in the counsellor's house. Clients will also be encouraged to seek post-test advice from the CBDA, which can be "generic" (i.e. not results based) or results-based.

Kits will be replaced by the PHC clinic supervisors on presentation of used kits, and following inspection of an HIV test logbook to confirm recording of names and addresses, but not results, of clients. Numbers of used kits, and results on late re-read, will be recorded by the CBDA/PHC supervisor. HIVST logbooks will be kept at the CBDAs home in a locked container.

There are no sharps or hazardous materials.

Couple's testing will be encouraged. In the case of couples wanting to self-test together, both partners will be asked to attend the IEC session, but clients will also be allowed to take up to 2 kits home if the partner cannot attend.

Testing of children (aged 15 years or less) will not be permitted as part of this trial, but can be arranged through special arrangement with the PSI Supervisors. For CBDAs participating in the **Home-initiation Arm** of the second stage randomisation, additional training will be provided on how to advise the client about the availability of this option, and the need to share a provisionally positive HIVST result in order to access this option.

Once a client requests home assessment, the CBDA will be responsible for arranging a clinical (ART trained nurse) visit to the participant's home or designated meeting point within 3 days to carry out confirmatory HIV testing, WHO staging, CD4 cell count (Alere PIMA CD4), and TB screening. They will also provide 2 weeks of Co-trimoxazole and ART if the participant meets eligibility requirements. Participants will then be provided with a completed ART registration card and follow-up appointment at the ART clinic.

5.4.2 Participant selection, inclusion and exclusion criteria

The inclusion criteria for clients are:

- Age 16 years or above
- Usual residence within a study PHC catchment area
- Able and willing to provide oral consent to HTC

The exclusion criteria for participation in the ACF intervention will be:

- Age 15 years or below
- Usual residence outside of the intervention cluster

5.4.3 VMMC mobilisers and Tunza Network

Using adaptations of the methods developed for the main CDBA trial, training packages, IEC materials, use of returned kits plus SQC for quality control, and social harms reporting

will be used to evaluate the potential role for HIVST delivered through VMMC mobilisers and the Tunza Network.

PSI-VMMC mobilisers will be trained to offer HIVST kits to men ages 15 to 49, who are the target of VMMC campaigns. Research evaluation will be limited to safety reporting aspects and analysis of the effect of introducing this method through comparison of beforeafter time trends in demand for VMMC at any given VMMC site, using a difference-in-differences analysis approach.

The Tunza Network are a social franchise of private practitioners who use with PSI reproductive health products. Tunza practitioners will be trained to offer HIVST kits to their patients. Research evaluation will be limited to safety reporting and analysis of the effect of introducing this method through comparison of before-after time trends in demand for ART referrals at any given Tunza site, using a difference-in-differences analysis approach.

5.5 Health economics

5.5.1 Costing studies

Costing will estimate the societal-level costs of providing HIVST interventions, both from the perspective of the health provider and the user. The MLW-LSHTM team will also collect costs on current MoH HIV prevention, testing and counselling, and treatment services.

The costing study will feed into estimates of cost-effectiveness, which are to be projected on different time scales and population levels. The first cost-effectiveness study will be a short-term, trial-based evaluation using costs and impacts directly measured within the scope of PSI HIVST distribution. The second study will be model-based and explore the long-term population costs and effects at scale using mathematical modelling.

Costing data will be collected initially within the CBDA evaluation villages, but will be expanded to all locations where PSI will be distributing HIVST kits through CBDA, peer, Tunza, and VMMC mobiliser models.

5.5.2 Study period

The costing study will run in parallel with the distribution of HIVST kits by PSI. During this period, MLW-LSHTM will collect programmatic expenditure data from PSI on a monthly basis. Data on user costs of accessing HIVST and HTC services will be gathered through the extended baseline questionnaire administered to adults living in Evaluation Villages.

Data from relevant HIV prevention, testing, and care facilities will be extracted throughout the project period, with data from ART clinics obtained from interview of staff and analysis of primary care clinic and District expenditure records, with permission of MOH and DHOs.

5.5.3 Study population and study size

Full financial and economic costs from the providers' perspective will be collected through PSI and MoH facilities. User costs of accessing existing and new forms of HIV testing and

linkage to care will be gathered using the extended baseline questionnaire, which will be assigned to a random sample of ~ 1000 enumeration participants.

5.5.4 Data Collection

Costing tools will be used in conjunction with service-related financial and activity reports in order to determine the unit costs of providing HTC and subsequent HIV care. Obtaining costs from MoH will require permission from MoH and District Health Officers (DHO). MLW-LSHTM will also carry out detailed micro-costing, including time and motion studies, to clinics assigned to the intervention and control arms of the impact evaluation. This is important in order to identify instances of reduced crowding in ART clinics due to HIVST decentralisation.

Full PSI costs for HIVST distribution will be derived from programme expenditure reports, while user costs will be collected through questions asked on service utilisation costs in the extended baseline questionnaire.

5.5.5 Data analysis

Gathered costing data will be used to conduct an economic evaluation, using decisionanalytic modelling, to compare the costs of the different HIVST models to current MoH HTC models. Key outcomes include the incremental cost per Disability Adjusted Life-Year (DALY) averted, which will allow the cost-effectiveness of HIVST and linkage to care models to be determined.

Additionally, a model of scale-up costs will be developed that takes into consideration budgetary constraints. This will include costs from the providers' perspective, but also changes in total societal costs once user costs have been taken into account.

5.6 Outcome evaluation

5.6.1 Data Capture

Four data collection channels will be employed for the impact evaluation:

- 1. Pre- and post-intervention household surveys
- 2. CBDA registers and forms
- 3. ART clinic registers and forms, and
- 4. Harms monitoring records.

Data will be collected using tablet computers and paper-based forms.

CBDA logbooks and forms

Process data on HIVST distribution by CBDAs will be captured using HIVST logbooks (date, name, village and number of test-kits taken), returned kits, self-completed questionnaires (SCQ), and self-referral cards for ART clinics.

The SCQ will include questions about the self-read HIVST result, satisfaction, coercion, and HIV testing and ART history. The returned kits will be collected and read against the SCQ by field supervisors before disposal. This will allow the study team to conduct confirmatory readings of HIVST results and provide an ongoing measure of accuracy. CBDAs will also use registers to track the age, sex and HIV and ART history of participants and the nature of support received for HIVST.

ART registers and forms

To monitor the number of referrals, HIV diagnoses and ART initiations, the study will extract routine facility records and, if applicable, self-referral cards from ART clinics serving the evaluation villages.

Harms monitoring records

Identified community leaders will provide weekly reports of deaths and any known episodes of domestic violence. CBDAs will then investigate any possible links to HIVST.

Data capture forms and questionnaires are shown in the Appendices

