1.4 Methodology

A population-based CRT with associated mixed methods sub-studies. The intervention will be delivered through CBDAs, trained by PSI to provide HIVST in their rural villages. 20 ART Clinics and their catchment populations will be randomised to either HIVST or standard of care (SOC) arms. The ~200 CBDAs in the HIVST arm will be trained to provide HIVST (OraQuick ADVANCE HIV I/II test kits, packaged for self-use) along with reproductive health products. CBDAs will provide brief pre-test information and a self-referral form with all kits to facilitated linkage into HIV care and prevention services. Posttest advice will be provided for all who confide positive HIVST results.

Outcomes will be captured at 12 months through:

- 1. Household level surveys (~5,000 adults) at baseline and after 12 months of intervention .These will include questions on recent HIV testing through any modality (**Primary Outcome**).
- 2. ART clinic records to investigate whether or not population-level demand for ART has increased (**Secondary Outcome**).

A second stage randomisation of HIVST CBDAs will further explore the role of homebased HIV care assessment for encouraging disclose of positive HIVST results and ART initiation. This is an implementation research study, and no biological specimens will be required for research other than for pilot accuracy evaluation.

The study will be preceded by pilot studies to test the ability to interpret pictorial instructions and accurately use and interpret HIVST kits (packaged with instructions in Chichewa). The trial will be accompanied by economic evaluations. Interviews with key informants will be used to explore the policy and regulatory landscape for HIVST. Tools developed for the main study will be evaluated in other community volunteer cadres, notably voluntary medical male circumcision mobilisers.

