Rural and peri-urban populations	25,000	96,000	121,000	Blantyre, Mwanza, Machinga, Thyolo	CBDAs
Tunza social franchise clients	3,600	27,000	30,600	Mchinji, Lilongwe, Salima, Dedza, Nkhotakota, Kasungu	Tunza providers
Potential VMMC clients	1,500	4,800	6,300	Blantyre	VMMC mobilisers
2. Key populations					
MSM	540	2,592	3,132	Blantyre, Lilongwe, Mzuzu	MSM peer educators
SSWs	1,728	8,294	10,022	Blantyre, Lilongwe, Mzuzu	FSW peer educators
Total	32,368	138,686	171,054		

Figure 3. Breakdown of target populations

*Includes cases of repeat testing with the same individual.

3. Research question, aims, objectives

HIVST research findings have so far have been limited to a single delivery model in urban Blantyre. Findings such as acceptability and accuracy of HIVST may not be generalizable to other target populations, including rural adults, and may also change along with cost and cost-effectiveness when different service delivery models are used.

Here we investigate the uptake, acceptability, safety, population-impact and costs of adding HIVST to the remit of two existing cadres of community volunteers working in Malawi:

- 1. Rural-based community-based distribution agents (CBDAs) who provide reproductive health and child survival commodities through social marketing in rural areas.
- 2. VMMC mobilisers who provide information on voluntary male circumcision services.

The main research questions to be addressed are

- Does HIVST provided through multifunctional community volunteers maintain high willingness to self-test, safety, accuracy, and acceptable uptake of post-test services?
- Does adding HIVST to reproductive health CBDA services increase coverage of recent HIV-testing at population-level?
- Does adding HIVST to reproductive health CBDA services increase demand for ART?
- Does the offer of home assessment and HIV care initiation improve linkage into post-test services?
- What are the social effects (benefits and harms) of introducing HIVST through community health
- What are the incremental costs and cost-effectiveness of adding community-based HTC?

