5.6.4 Outcome evaluation

For the comparison of **coverage of recent** / **ever HIV testing**, outcomes will be evaluated through household surveys as detailed above.

For evaluation of **ART initiations within study area villages**, maps showing study area boundaries and names of participating villages will be produced and displayed in HCT and ART clinics. ART register completion will be adjusted in collaboration with MoH to allow previous HIVST / home-initiation episodes to be documented in the "Comments" column.

Clinic staff will be asked to ensure that all clients are asked directly if they are attending following HIVST results and that the village of residence is clearly recorded in the ART register. The self-referral cards, which are presented by the participants to the clinic, will contain spaces for ART clinic staff to log confirmatory results, the national ART number for clients entering HIV care, and any other relevant referrals (e.g., VMMC).

PSI CBDA supervisors will extract these data on a monthly basis from each of the 20 ART clinics included in the study. Retrospective data extraction will also be used to provide an indication of pre-intervention ART initiations from the 20 study clinics.

In **Home-Initiation villages**, where participants have the option of requesting home initiation of care, PSI CBDA supervisors will fill out HIV care registration cards and maintain a logbook allowing cross-reference by ART number with the local ART clinic. Total numbers of clients confiding positive HIVST results will be recorded by all CBDAs in post-test logbook recording disclosure and other referral events without name.

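### The late re-read of returned kits measures agreement between two readings of one strip, not the accuracy that Section 5.6.1 claims for it

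*Protocol*

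**What the plan says.** On data capture, Section 5.6.1 states: "The returned kits will be collected and read against the SCQ by field supervisors before disposal". On the questionnaire: "The SCQ will include questions about the self-read HIVST result". On the purpose: "This will allow the study team to conduct confirmatory readings of HIVST results and provide an ongoing measure of accuracy".

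Section 5.4.1 adds how the kits come back and when they are read: "Clients will be encouraged to return their used kits confidentially to the CBDA", in person or in a sealed envelope, and "Numbers of used kits, and results on late re-read, will be recorded by the CBDA/PHC supervisor". The SCQ is supplied in the envelope meant for the used kit. Neither section gives an interval between test and re-read, or says whether the strip is read before the SCQ is seen. The only masking text, in Section 5.3, concerns trial arm.

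Section 1.4 says that "no biological specimens will be required for research other than for pilot accuracy evaluation". The pilot (Section 5.1.4) follows self-testing with parallel finger-prick blood tests, and its precision table (Section 7.1) is for concordance with confirmatory tests.

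The first research question in Section 3 asks whether HIVST given through community volunteers will "maintain high willingness to self-test, safety, accuracy, and acceptable uptake of post-test services". Section 5.8.4 uses the re-read, together with results shared with CBDAs, to count new HIV-positive cases.

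**The concern.** Accuracy means agreement with true HIV status. A second look at the same strip cannot supply that. If a client's handling of the test produced a wrong strip, both readers can read it correctly and agree on a wrong answer. If the supervisor knows the client's answer, the second reading is not independent either. If the strip changes before it is re-read, the change is scored as a client error. The measure also covers only clients who choose to return a kit.

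At stake is a claim on a stated research question. A figure reported under the heading of accuracy for volunteer delivery would be taken as comparable with the pilot's, although the two measure different things. The same late reading enters the count of new cases, so a strip that gains a line after the client's reading could add a case that was never there.

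**Working it through.** **1. The two meanings of accuracy side by side.**

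| | Pilot (5.1.4, 7.1) | Trial phase (5.4.1, 5.6.1) |
|---|---|---|
| Setting | Supervised, two villages outside the main study | CBDA delivery |
| Second reading | Counsellor, following the self-test | Supervisor, late, interval not given |
| Reference | Parallel blood-based tests; ELISA if discordant | None: the client's own answer |
| Coverage | Participants who accept HIVST and HTC | Kits voluntarily returned |
| Stated precision | Yes | None |

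**2. The plan's own figures.** No figure is stated for the re-read, so there is none to reproduce. The nearest are the pilot's. Exact binomial 95% intervals give 91.0% to 97.6% for 190/200 and 95.0% to 99.5% for 196/200, as stated in Section 7.1. All nine filled cells reproduce to within 0.1 point. The pilot's accuracy measure is sound as specified.

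**3. Which way agreement errs.** This is an illustration of direction only. From the protocol: prevalence π = 10.2% (Section 2, a national estimate). Assumed, with no source in the protocol: strip sensitivity se of 85% to 100%; strip specificity 99.5%; clients misread 5% of positive and 0.5% of negative strips; a share d of negative strips (0 to 5%) looks positive by the re-read; a share c of conflicting re-reads (0 to 100%) is changed to match the SCQ.

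- Share of positive strips: P = π·se + (1−π)·0.005.
- Accuracy of the client's reading: A = π[0.95·se + 0.005(1−se)] + (1−π)[0.995·0.995 + 0.005·0.05].
- Agreement, masked reader: G0 = 0.95·P + (1−P)[0.995(1−d) + 0.005·d].
- Agreement with deference: G = G0 + c(1−G0).

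At se = 85%: P = 0.0867 + 0.0045 = 0.0912, and A = 0.102·0.80825 + 0.898·0.990275 = 0.972. With d = 0, G0 = 1 − 0.05·0.0912 − 0.005·0.9088 = 0.991. The client's sensitivity is only 0.808, and agreement does not show it.

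| se | Accuracy | d=0, masked | d=3%, masked | d=5%, masked | d=3%, c=50% | c=100% |
|---|---|---|---|---|---|---|
| 85% | 97.2% | 99.1% (+1.9) | 96.4% (−0.8) | 94.6% (−2.6) | 98.2% (+1.0) | 100% (+2.8) |
| 100% | 98.6% | 99.0% (+0.4) | 96.4% (−2.2) | 94.6% (−4.0) | 98.2% (−0.4) | 100% (+1.4) |

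Brackets show agreement minus accuracy, in percentage points. The sign depends on strip error, late change and deference, and the planned data identify none of the three. Selective return, which is not modelled, could act in either direction.

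**4. The case count.** Section 5.8.4 takes new cases from the re-read as well as from disclosure. A negative strip that gains a line adds an apparent case. The protocol gives neither the rate of change nor the delay, so no size can be put on this.

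**The case against.** The strongest reply is that this is process monitoring. Section 5.6.1 introduces these items as process data, Section 5.4.3 describes the same use of returned kits as quality control, and accuracy is not a primary or secondary outcome in Section 4.3. Formal accuracy belongs to the pilot, which has a reference test, stated precision and a rule for repeating the study. Section 5.6.3 leaves quality-assurance detail to SOPs, where the reading order may be fixed. All of this stands, and it limits the weight of the point. It does not rescue the wording of Section 5.6.1, which claims accuracy for the trial phase.

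Four stronger readings are tempting, and the documents do not support them.

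- *That the accuracy figure will be falsely high.* Late line change works the other way, and the table shows both signs.
- *That the re-reader is shown to be unblinded.* The text says that kits are read against the SCQ. With both in one envelope, that is a strong inference, but the order is not stated.
- *That Sections 5.4.1 and 5.6.1 contradict each other on the reader.* One says who records and the other who reads; these may be the same staff.
- *That the accuracy question rests on the re-read alone.* The pilot addresses it, though under supervision. Home assessment (5.4.1) includes confirmatory testing, and self-referral cards (5.6.4) "will contain spaces for ART clinic staff to log confirmatory results". Both reach only clients who disclose or link.

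**Conclusion.** The concern holds as a matter of measurement and labelling. The re-read gives agreement between the client's reading and a late second reading among returned kits. It has no independent reference and no stated masking to the SCQ, so it should not be called confirmatory or a measure of accuracy. This rests on the protocol's text and not on the assumed inputs. The direction and size of its error as a proxy for accuracy are unknown, and the illustration is not evidence of either.

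The primary outcome is untouched. What is affected is the accuracy part of the first research question as it applies to volunteer delivery, and the count of new HIV-positive cases. Later analysis cannot restore an independent reading or create a reference standard, so the change belongs in data capture.

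**What to change.** 1. In Sections 5.4.1 and 5.6.1, have the supervisor record the strip reading and its date before seeing the SCQ, and compare the two afterwards. Take time since kit distribution from the logbook date.
2. In Section 5.6.1, replace the confirmatory and accuracy wording with *agreement between self-reading and late re-reading among returned kits*. Report the return fraction (kits returned over kits distributed). Base accuracy claims on the pilot.
3. As a supplement, report the proportion of self-test positives confirmed, from the home-assessment tests and the self-referral cards. State that it covers only clients who disclose or link, and that it cannot detect false negatives.
4. In Section 5.8.4, report cases found only by late re-read separately from cases disclosed or confirmed.

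The cost is a change to SOPs, forms and wording, with no new specimens or staff. The limitation that remains, and should be stated, is that field accuracy among clients who test negative rests on the supervised pilot.

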6.1. HIVST

HIV testing and counselling including HIVST is well established, and known to have a high level of safety and favourable risk: benefit ratio. However, harmful reactions can occur. For the purposes of this trial, we will focus on capture of the following **Serious Adverse Events.**

- Death or hospitalisation due to self-inflicted injuries within 30 days of a positive HIVST results
- Death or hospitalisation resulting from violent assault by others (intimate partner violence, assault by family members, assault by community members) within 30 days of a positive HIVST result

Deaths and hospitalisations will be captured through the Social Harms System established in each cluster. The PSI Supervisor will interview the client and relatives to establish relatedness where possible.

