Pilot extended baseline questionnaire and revise based on feedback	PI/PM	PSI/MLW																					
Conduct extended baseline questionnaire	PM/PI	PSI/MLW										1											
Conduct quality and accuracy checks on incoming electronic data	PI/DM	MLW																					
Clean quantitative data	DM/PI	MLW										Ì											
Conduct preliminary analysis of quantitative data	PI/LC/MN	MLW/LSHTM										Ì											
Generate preliminary report on baseline findings	PI/LC	MLW																					
Conduct in-depth analysis of quantitative data	PI/LC/MN	MLW/LSHTM																					
Generate in-depth report on baseline findings	PI/LC	MLW																					
Collect and analyse data for interim household survey																							
Pilot extended interim household survey and revise based on feedback	PI/PM	PSI/MLW																					
Conduct interim household survey	PM/PI	PSI/MLW																					
Conduct quality and accuracy checks on incoming electronic data	PI/DM	MLW																					
Clean quantitative data	DM/PI	MLW																					
Conduct preliminary analysis of quantitative data	PI/LC/MN	MLW/LSHTM																					
Generate preliminary report on interim findings	PI/LC	MLW																					

	1	1	1	 	-	1	1	() (1	ſ	 	1			i	1	
Conduct in-depth analysis of quantitative data	PI/LC/MN	MLW/LSHTM		 								 						
Generate in-depth report on interim findings	PI/LC	MLW																
Collect and analyse data from CBDAs and ART clinics																		
Pilot CBDA tools in intervention villages and revise																		
based on feedback	PI/PM	MLW/PSI		 														
Collect SCQs and HIVST registers and kits from CBDAs in intervention villages	PI/PM/CC	MLW/PSI																
Collect harms monitoring records from community	PI/PIVI/CC	IVILVV/P3I										 						
leaders in intervention villages	PI/PM/CC	MLW/PSI																
Collect patient registers and referral forms from ART	, ,																	
clinics	PI/PM/CC	MLW/PSI																
Enter paper-based data into electronic files	DM	MLW																
Conduct quality and accuracy checks on incoming																		
electronic data	PI/DM	MLW		 	_													
Clean quantitative data	DM/PI	MLW																
Conduct preliminary analysis of quantitative data	PI/LC/MN	MLW/LSHTM																
Generate preliminary report on impact evaluation									Ì									
findings	PI/LC	MLW		 														
Conduct in-depth analysis of quantitative data	PI/LC/MN	MLW/LSHTM																

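### Section 6.1 places harms capture in every cluster, but the work plan collects harms records in intervention villages with no SOC row, and the leaders' weekly report does not name two kinds of event that 6.1 defines as SAEs

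*Protocol*

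**What the plan says.** Three parts of the protocol describe how harms are recorded.

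- **Section 5.6.1** lists harms monitoring records as one of four data channels for the impact evaluation. It gives the content of the leaders' report: "Identified community leaders will provide weekly reports of deaths and any known episodes of domestic violence". It adds: "CBDAs will then investigate any possible links to HIVST". No arm is named.
- **Section 6.1** gives the scope: "Deaths and hospitalisations will be captured through the Social Harms System established in each cluster". It defines two groups of SAE. The first is "Death or hospitalisation due to self-inflicted injuries within 30 days of a positive HIVST results". The second is death or hospitalisation from violent assault, which covers "intimate partner violence, assault by family members, assault by community members) within 30 days of a positive HIVST result".
- **Section 14 (work plan, part A)** has a task that runs over two lines: "Collect harms monitoring records from community", continued as "leaders in intervention villages". There is no matching task for SOC villages.

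Section 10.1 adds a community reporting network and a hotline for HIVST participants. Section 3 includes among the main research questions: "What are the social effects (benefits and harms) of introducing HIVST through community health".

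**The concern.** The safety section and the work plan disagree on where harms are recorded. Field teams work from the work plan, and a weekly report that was never collected is hard to reconstruct a year later.

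Deaths and domestic violence occur in villages whether or not HIVST is offered. A total from the HIVST arm alone cannot show whether HIVST raised them, lowered them or left them unchanged. The randomised design could answer that question, but only if both arms report in the same way.

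There is a second, separate mismatch. The content given for the leaders' report is narrower than the events that 6.1 defines as serious.

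**Working it through.** The protocol states no rate, sample size or power for harms, so there is no figure to reproduce. The check is a comparison of texts.

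**1. Which clusters report?**

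- The unit of randomisation is the clinic with its catchment (section 4.1). There are 20 clusters (section 5.8.5), 10 per arm (section 7.2). Taken literally, the wording of 6.1 covers all 20.
- The work-plan task names intervention villages. The task just above it, on self-completed questionnaires, HIVST registers and kits, uses the same phrase, and those items exist only in the HIVST arm. The task just below it, on ART clinic registers, is needed from both arms and carries no such limit. The natural reading of the harms task is therefore the HIVST arm.
- Under 6.1, 20 of 20 clusters report. Under the work plan, 10 of 20 report and the SOC arm supplies 20 − 10 = 10 fewer. With no SOC counts, no rate ratio for deaths or domestic violence can be estimated.

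**2. Which events does the described weekly report name?**

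| Cause (6.1) | Death | Hospitalisation |
|---|---|---|
| Self-inflicted injury | named (deaths) | not named |
| Intimate partner violence | named (deaths) | named if known (domestic violence) |
| Assault by family members | named (deaths) | largely named if known (domestic violence) |
| Assault by community members | named (deaths) | not named |

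The other routes do not clearly fill the two gaps. The hotline (10.1) depends on a participant calling. The self-completed questionnaire (5.6.1) asks about coercion and reaches only kit users. Supervisors' spot-check home visits (5.6.3) are described as quality assurance, with no harm items mentioned. The community network (10.1) could reach these events, but the only content given for leaders' reports is that in 5.6.1. The Forms and Tools Guide lists no harms form.

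**3. Which events can be compared between arms?**

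- Both SAE groups require a positive HIVST within the previous 30 days. SOC CBDAs give out no kits (section 4.1), so these SAEs can hardly arise in SOC clusters, even with full reporting there.
- Only events defined without reference to HIVST can be compared: all deaths, domestic violence, and hospitalisation for self-injury or assault.
- Suicide alone would be too rare. Section 6.2 cites none in 27,000 episodes. The one-sided 95% upper bound is 1 − 0.05^(1/27,000) = 0.000111, about 1.1 per 10,000. Over the 34,068 episodes in section 1.2 this is 0.000111 × 34,068 ≈ 3.8 expected events at most. Over the 121,000 CBDA self-tests targeted in section 2.3.3 it is about 13.4. This assumes that the earlier experience carries over.
- Domestic violence may be common enough to compare, but the protocol gives no rate, so its precision cannot be computed.

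**The case against.** The strongest reply is that 6.1 is the operative safety text and already covers every cluster. Section 5.6.1 names no arm, and neither does the statement in 10.1 that monitoring runs throughout distribution. Against these stands a single work-plan row that does not say that SOC villages are excluded. The protocol also uses the word intervention loosely: section 5.2.1 says that all 20 clinics are included in the intervention. This stands in part. The row is ambiguous, and one-arm reporting follows only if the work plan governs. It does not remove the conflict, and the neighbouring tasks favour the HIVST-arm reading.

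Four stronger readings are tempting, and the documents do not support them.

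- *That the trial has no comparator for harm.* This is conditional on the work plan being followed; 6.1 says otherwise.
- *That the trial misses its own SAEs.* Section 6.1 states that hospitalisations are captured, and 10.1 adds two further routes. What is missing is any described report that actively asks for two kinds of event.
- *That two of the eight cells in the table measure the share of events missed.* The cells are not weighted by frequency and describe one sentence of the protocol.
- *That the Data Safety Monitoring Board would see one arm only.* Section 5.3 speaks of outcome data and does not mention harms records. The survey and ART outcomes come from both arms.

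It is also fair to say that harms are neither the primary nor the secondary outcome, and that the protocol does not expressly promise a randomised comparison of them. That limits the weight of the point. But the protocol makes harms records an impact-evaluation channel and social harms a main question, so comparable counts in both arms are a reasonable expectation.

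**Conclusion.** Two inconsistencies stand. First, 6.1 and the work plan disagree on whether harms are recorded in 20 clusters or in the 10 HIVST clusters. If the work plan is followed, deaths and domestic violence cannot be compared by arm. Second, the weekly report as described does not name hospitalisation for self-inflicted injury or hospitalisation after assault by community members, although 6.1 counts both as SAEs.

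The size in events is unknown, because no rates are given. The conclusion assumes that the work-plan wording means the HIVST arm, and that the actual weekly form, which is not available here, asks no more than 5.6.1 describes. The point should be corrected before reporting starts. It does not touch the primary or secondary outcome.

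**What to change.** 1. Reconcile the work-plan row with 6.1, so that community leaders in all 20 clusters, HIVST and SOC, complete the same weekly form.
2. Add two lines to that form: hospitalisation for self-inflicted injury, and hospitalisation after any assault.
3. Tabulate deaths, domestic violence and these hospitalisations by arm for all adult residents, regardless of HIVST use.
4. Keep the SAEs that depend on a positive HIVST as a descriptive listing for the HIVST arm, not as a between-arm contrast.

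The cost is one work-plan row, two form lines and a weekly report from SOC leaders, which 6.1 already implies. No new household-survey questions are needed; questions on violence there would be a separate and sensitive addition.
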